### **5.3.1.1                    Study Procedures**

The study procedures outlined in [Table 2](#) and [Table 4](#) are discussed in detail in this section, with the exception of in vivo pharmacodynamic biomarkers (discussed in Section [5.3.1.2.1](#)), exploratory research and validation studies (discussed in Section [5.3.1.2.2](#)), drug concentration measurements (discussed in Section [5.3.2](#)), the collection of prior and concomitant medication information (discussed in Section [5.2.3](#)), and the collection of AE information (discussed in Section [6.0](#)). All study data will be recorded in source documents and on the appropriate eCRFs.

#### **Informed Consent**

At the Screening visit, the subject will sign and date a study specific, IEC/IRB approved, informed consent form for the study (i.e., includes both Periods 1 and 2) before any study procedures are performed or any medications are withheld from the subject in order to participate in this study. Separate written consent will be required for each subject in order to participate in the optional exploratory research and validation studies. Subjects can withdraw informed consent at any time.

Details regarding how informed consent will be obtained and documented are provided in Section [9.3](#).

#### **Inclusion/Exclusion Criteria**

Subjects will be evaluated to ensure they meet all inclusion criteria and have none of the exclusion criteria at both Screening and Baseline Visits.

#### **Medical and Surgical History**

A complete non-RA-related medical and surgical history, including history of alcohol and nicotine use, will be taken from each subject during the Screening Visit. Additionally, a list of each subject's specific RA-related medical and surgical history will be recorded at Screening. History of herpes zoster, herpes zoster vaccination, and hepatitis B vaccination status will be recorded as part of the medical history. An updated medical

history will be obtained prior to study drug administration at Baseline, to ensure the subject is still eligible for enrollment.

A detailed medical history with respect to TB risk factors will be documented in the study source documentation. This information will include BCG vaccination, cohabitation with individuals who have had TB, and travel to, residence in, or work in TB endemic locations.

### **Patient Questionnaires**

Subjects will complete the following questionnaires as specified in [Table 2](#) and [Table 4](#); a validated translation will be provided in their local language, as applicable:

#### *Period 1 and Period 2*

- Patient's Global Assessment of Disease Activity Visual Analog Scale (VAS) ([Appendix F](#))
- Patient's Assessment of Pain Visual Analog Scale (VAS) ([Appendix G](#))
- Health Assessment Questionnaire – Disability Index (HAQ-DI) to assess the physical function and health-related quality of life of each subject ([Appendix H](#))
- Patient's Assessment of Severity and Duration of Morning Stiffness Numerical Rating Scale (NRS) ([Appendix I](#))\*
- EuroQoL-5D-5L (EQ-5D-5L) ([Appendix J](#))
- Short Form-36 (SF-36) ([Appendix K](#))
- Functional Assessment of Chronic Illness Therapy – Fatigue (FACIT-F) ([Appendix L](#))
- Work Instability Scale for RA (RA-WIS) ([Appendix M](#))

\* Paper; all other patient-reported outcomes (PROs) collected electronically.

The subject should complete the questionnaires before site personnel perform any clinical assessments and before any interaction with site personnel has occurred to avoid biasing the subject's response.

### **TB Testing/TB Prophylaxis**

#### *Period 1*

The TB screening tests are diagnostic test results to be interpreted in the context of the subject's epidemiology, history, exam findings, etc., and it is the responsibility of the Investigator to determine if a subject has previous, active, or latent TB.

At Screening, all subjects will be assessed for evidence of increased risk for TB by a risk assessment form ([Appendix E](#)) and tested for TB infection by an Interferon-Gamma Release Assay (IGRA; QuantiFERON®-TB Gold) test. The PPD Skin Test should be utilized only when a QuantiFERON®-TB Gold Test is not possible for any reason (unless both tests are required per local guidelines). The site staff will complete the TB risk assessment form and enter the data into an appropriate eCRF. The assessment for TB risk and TB test will be repeated at Premature Discontinuation visit.

Preferred Method:

- QuantiFERON®-TB Gold Test will be analyzed by the central laboratory (QuantiFERON® test is preferred over PPD skin).
- If the QuantiFERON®-TB Gold Test is NOT possible (or if both the QuantiFERON®-TB Gold Test and the PPD Skin Test are required per local guidelines): the PPD Skin Test (also known as a TB Skin Test) will be performed according to standard clinical practice. The TB Skin Test should be read by a licensed healthcare professional between 48 and 72 hours after administration. A subject who does not return within 72 hours will need to be rescheduled for another skin test. The reaction will be measured in millimeters (mm) of induration and induration  $\geq 5$  mm for RA subjects is considered a positive reaction. The absence of induration will be recorded as "0 mm" not "negative." Subjects who have had an ulcerating reaction to the TB Skin Test

in the past should not be re-exposed and should not be tested by a PPD skin test.

If a subject had a negative QuantiFERON®-TB Gold (and/or PPD) test (or IGRA equivalent such as T-SPOT TB test) within 90 days prior to Screening and source documentation is available, the test does not need to be repeated, provided nothing has changed in the subject's medical history to warrant a repeat test. These cases may be discussed with the AbbVie TA MD. The results of the TB test(s) will be retained at the site as the original source documentation.

In the event both a PPD test and a QuantiFERON®-TB Gold test are performed, the result of the QuantiFERON®-TB Gold test will supersede the result of the PPD test unless otherwise required by local guidelines. If the QuantiFERON®-TB Gold test is indeterminate, the site should repeat the test with another blood sample. If the second QuantiFERON®-TB Gold test is also indeterminate, the subject is considered to be positive. At a site with capacity to perform both tests, if a PPD is placed as the only form of TB test at Screening, then the TB test to be used for the remainder of the study for that subject is the PPD. Similarly, if a subject enters the study with a QuantiFERON®-TB Gold test alone or other IGRA (negative result), then the subject should have their annual TB test performed with the QuantiFERON®-TB Gold test.

Subjects with a negative QuantiFERON®-TB Gold test (and/or negative PPD TB skin test) and chest x-ray (CXR) not suggestive of active TB or prior TB exposure may be enrolled.

Subjects with a positive TB test must be assessed for evidence of active TB versus latent TB, including signs and symptoms and CXR. Subjects with no signs or symptoms and a CXR not suggestive of active TB may be enrolled after initiation of TB prophylaxis (see below). Subjects with evidence of active TB must not be enrolled.

At Screening, if the subject has evidence of latent TB infection (QuantiFERON®-TB Gold test and/or the PPD test positive) and has a CXR not suggestive of active TB, prophylactic

treatment must be initiated at least 3 weeks prior to administration of study drug per local guideline in Japan. The prophylaxis needs to be completed, however, the full course of prophylaxis does not need to be completed prior to the first dose of study drug. If the Investigator deems that it is necessary, consultation with a TB expert could be considered.

**Of note: Rifampicin or Rifapentine are not allowed for TB prophylaxis.**

Subjects with a prior history of latent TB that have documented completion of a full course of anti-TB therapy within 1 year prior to first study drug administration will be allowed to enter the study provided nothing has changed in the subject's medical history to warrant repeat treatment.

Subjects with documented completion of a full course of anti-TB therapy greater than 1 year prior to first study drug administration may be allowed to enter the study only after consultation with the AbbVie TA MD.

Newly initiated prophylactic treatment should be captured in the eCRF and in the source documents. Prior therapy should be captured in the eCRF.

*Period 2*

Subjects with documentation of prior positive result of QuantiFERON-TB Gold Test (or equivalent) and/or PPD are not required to repeat either TB test during the study and should be considered positive. The TB risk assessment form will be completed annually for all subjects, regardless of TB test results.

For subjects with a negative QuantiFERON®-TB Gold (and/or PPD) test at Screening, a QuantiFERON®-TB Gold (and/or PPD) re-test will be performed (or both if required by local guidelines) annually and at PD.

If one of the annual tests has a positive test result (seroconversion), a chest x-ray (CXR) needs to be performed as soon as possible to aid in distinguishing active versus latent TB.

If the QuantiFERON-TB Gold test is indeterminate, then the investigator should perform a local QuantiFERON-TB Gold test (or through the central laboratory if not locally available) to rule out a positive test result. If testing remains indeterminate or is positive, then the subject is considered to be positive for the purpose of this study. If the testing result is negative, then the patient is considered to be negative.

Expert consultation for the evaluation/management of TB may be considered per Investigator's discretion.

Any positive TB screen after the patient has started the study, should be reported as an adverse event (AE) of latent TB or active TB (as applicable).

Obtain a CXR annually for subjects with TB risk factors as identified by the TB risk assessment form ([Appendix E](#)) or for subjects living in areas endemic for TB or for subjects with newly positive PPD or QuantiFERON®-TB Gold test.

During the study, subjects with new evidence of latent TB should initiate prophylactic treatment immediately per local guidelines and complete at least 6 months of prophylaxis. TB prophylaxis should be initiated and study drug(s) should not be withheld. Two to 4 weeks later (per local guidelines), the subject should be re-evaluated (unscheduled visit) for signs and symptoms as well as laboratory assessment of toxicity to TB prophylaxis.

Newly initiated prophylactic treatment and prior therapy should be captured in the eCRF.

If the subject is experiencing signs or symptoms suspicious for TB or something has changed in the subject's medical history to warrant a repeat test before the next scheduled annual TB re-test, the case (including the TB test results) must be discussed with the AbbVie TA MD.

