**Table 2. Study Activities (Period 1) (Continued)**

- c. This visit is 30 days after last dose of study drug for those subjects who complete Period 1 and do NOT enter Period 2 or for those subjects who prematurely discontinued study drug and study participation. A 30-day follow-up phone call may be allowed for subjects who have already completed PD visit to determine the status of any ongoing AEs/SAEs or the occurrence of any new AEs/SAEs.
- d. Obtain prior to performing any study related procedures.
- e. Note herpes zoster and hepatitis B vaccination status in medical history.
- f. Collect serious adverse events and protocol-related non-SAE that occur after a subject signs the informed consent, prior to the first dose of study drug.
- g. Prior to other procedures. For morning stiffness, duration will be captured only if NRS rating is  $> 0$ .
- h. Refer to Section 5.3.1.1 Study Procedures TB Testing for specific requirements for TB testing and TB Prophylaxis. The Latent TB risk factor assessment and TB Testing will be performed in case of Premature Discontinuation visit but not at Week 12.
  - i. The chest x-ray will not be required if a subject had a previous normal chest-x-ray within 90 days of Screening, provided that all source documentation is available at the site. (refer to Section 5.3.1.1 Chest X-Ray for specific requirements). Obtain chest x-ray at PD for subjects with TB risk factors as identified by the TB risk assessment form, or for subjects living in areas endemic for TB, or for subjects with a newly positive QuantiFERON-TB Gold test (and/or PPD skin test) after baseline.
  - j. For subjects with a normal ECG taken within 90 days of Screening, a repeat ECG at Screening will not be required, provided all source documentation is available. For subjects who do not enter Period 2 or prematurely discontinue from the study, an ECG will be performed. Refer to Section 5.3.1.1 12-Lead ECG for additional details.
  - k. Blood pressure, pulse rate, body temperature, and respiratory rate should be performed before blood draws are performed.
  - l. A full physical exam is required at the visits indicated. A symptom-directed physical exam may be performed when necessary.

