**Table 4. Studies Activities (Period 2) (Continued)**

- b. This visit is 30 days after last dose of study drug for those subjects who complete Period 2 or for those subjects who prematurely discontinued study drug and study participation. A 30-day follow-up phone call may be allowed for subjects who have already completed PD visit to determine the status of any ongoing AEs/SAEs or the occurrence of any new AEs/SAEs.
- c. At Week 24 (after Week 24 assessments have been performed), if a subject fails to meet LDA criterion (LDA defined as CDAI  $\leq$  10) investigator should adjust the subject's background RA therapies. Initiation of or change in corticosteroids, NSAIDs, acetaminophen, or adding or increasing doses of csDMARDs (concomitant use of up to 2 csDMARDs except the combination of MTX and leflunomide; see Inclusion Criterion 3) is allowed as per local label.
- d. Prior to other procedures. For morning stiffness, duration will be captured only if NRS rating is  $> 0$ .
- e. TB testing should be performed every 48 weeks after Week 48 and at PD in subjects with previous negative Quantiferon and/or PPD tests. Subjects with new evidence of latent TB should initiate prophylactic treatment immediately per local guidelines. Refer to Section 5.3.1.1 TB Testing/TB prophylaxis for additional details.
- f. Starting at Week 48, obtain chest x-ray every 48 weeks for subjects with TB risk factors as identified by the TB risk assessment form, or for subjects living in areas endemic for TB, or for subjects with a newly positive QuantIFERON-TB Gold test (and/or PPD skin test) after baseline.
- g. Starting at Week 48, ECGs will be performed every 48 weeks and for subjects who prematurely discontinue from the study. An ECG may be performed at any visit if deemed necessary by the Investigator.
- h. Blood pressure, pulse rate, body temperature, and respiratory rate should be performed before blood draws are performed.
- i. A full physical exam is required every 24 weeks after Week 48. A symptom-directed physical exam may be performed when necessary.
- j. Starting at Week 24 and thereafter, subjects who failed to show at least 20% improvement in TJC and SJC compared to baseline at 2 consecutive visits should be discontinued from the study.
- k. CDAI calculation requires input of SJC28 + TJC28 + PtGA + PhGA into IRT system. At Week 24, investigator should optimize background RA therapies in subjects who failed to achieve CDAI  $\leq$  10.

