10.2.2.6 Adverse Events of Special Interests

The Adverse Events of Special Interests (AESI) categories will be summarized and presented by "as treated" treatment group and overall using SOC and MedDRA PT. The AESI categories will be identified by the following search criteria per Standard MedDRA Queries (SMQs)/Company MedDRA Queries (CMQs) in [Table 13](#) below.

Table 13. AESI for Upadacitinib with SMQs/CMQs/PTs Searches

AESI	Type of MedDRA Query	Broad or Narrow Search	SMQ/CMQ Search Criteria
Serious Infections	CMQ		"Infections" – Subset for SAEs
Opportunistic Infection	CMQ		"Opportunistic Infection"
Malignancy	SMQ	Narrow	"Malignancies"
Non-Melanoma Skin Cancer (NMSC)	SMQ	Broad	Skin Malignant tumours (Broad SMQ) removing Melanoma CMQ
Malignancy excluding NMSC			Malignancy Narrow SMQ and removing NMSC output
Lymphoma	SMQ		"Malignant Lymphomas"
Hepatic Disorder	SMQ	Narrow	"Drug Related Hepatic Disorders"
Gastrointestinal Perforations	SMQ	Narrow	"Gastrointestinal Perforation"
Anemia	CMQ		"Non-Hemolytic and Non-Aplastic Anemias"
Neutropenia	CMQ		"Hematological Toxicity – Neutropenia"
Lymphopenia	CMQ		"Hematological Toxicity – Lymphopenia (Veliparib Product Specific)"
Herpes Zoster	CMQ		"Herpes Zoster"
Creatine Phosphokinase (CPK) Elevation	PT		Search only for the PT of "Blood creatine phosphokinase increased"
Renal Dysfunction	SMQ	Narrow	"Acute Renal, Failure"
Tuberculosis	CMQ		"Tuberculosis"
Adjudicated cardiovascular events	Output from CAC		

Additional AEs may be considered for tabulation/summary based on recommendations from Clinical and Safety as deemed appropriate.

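### If the Tuberculosis query includes latent TB, the long-term AESI rate mixes test conversions with disease, and its difference from placebo leans towards excess on drug

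*Protocol*

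**What the plan says.** **Reporting rule.** Protocol 5.3.1.1 (TB Testing/TB Prophylaxis, Period 2) states: "Any positive TB screen after the patient has started the study, should be reported as an adverse event (AE) of latent TB or active TB". The sentence adds that the label is whichever of the two applies. The same subsection deals with an indeterminate retest by a further test: "If testing remains indeterminate or is positive, then the subject is considered to be positive for the purpose of this study".

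**When tests are done.** In Period 1, Table 2 note h says: "The Latent TB risk factor assessment and TB Testing will be performed in case of Premature Discontinuation visit but not at Week 12". This holds in every arm. In Period 2, Table 4 note e says: "TB testing should be performed every 48 weeks after Week 48 and at PD in subjects with previous negative Quantiferon and/or PPD tests". Subjects with a documented earlier positive result "are not required to repeat either TB test during the study and should be considered positive". By Period 2 all subjects take upadacitinib.

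**How events are counted.** SAP 10.2.2.6 says: "The AESI categories will be identified by the following search criteria per Standard MedDRA Queries" and company queries. The Tuberculosis row of Table 13 names a company query of the same name; it gives no terms and does not limit the row to active disease. SAP 10.2.3 assigns each long-term event to the treatment taken at onset, so placebo time is Period 1 only. SAP 10.2.3.1 plans a difference in AESI rate per 100 patient-years, each dose against combined placebo, with a normal-approximation 95% CI. SAP 10.2.3.3 gives AESI rates by system organ class and preferred term.

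**The concern.** The two sides of the long-term comparison differ in the chance of finding a positive TB test. A subject who completes 12 weeks of placebo has no scheduled test while on placebo. The same subject is then tested during Period 2 on upadacitinib, and a conversion found there counts against the drug, even if it arose during the placebo weeks. If the query picks up latent TB, part of the Tuberculosis rate on drug comes from the test calendar.

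The two kinds of event have different meanings in the protocol itself. Active TB leads to withdrawal (5.4.1, 6.1.7); for new latent TB, prophylaxis is started and study drug is not withheld (5.3.1.1). A single line that pools them is hard to read as a safety signal. The SAP is version 1.0 of 31 August 2017. Protocol Appendix O lists the reporting rule among the additions of the later amendment (synopsis dated 23 February 2018), so the SAP text does not address it.

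**Working it through.** The documents give no TB rate or test yield, so there is no plan figure to reproduce. The check compares testing intensity and its consequence with no active TB anywhere.

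**Inputs**
- 48 subjects per group, placebo being 3 × 16 (Protocol 8.2, 8.3). Each dose is eventually taken by 48 + 16 = 64 subjects.
- Placebo lasts 12 weeks (84 days); dosing lasts about 3.5 years (Protocol 5.6.4).
- Drop-out is 5% (Protocol 8.2), applied here to Period 1.
- Assumed: a proportion q of tests, 0.5% to 3%, is positive or repeat-indeterminate; the query includes latent TB; all 64 subjects are retestable; no one leaves Period 2.

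**Exposure**
- Placebo: 48 × 84 / 365.25 = 11.0 PY.
- Each dose: 48 × 3.5 + 16 × (3.5 − 84/365.25) = 168 + 52.3 = 220.3 PY.

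**Tests**
- Table 4 note e can be read as a first retest at Week 48 or at Week 96. In 3.5 years (about 182 weeks) that gives three rounds (Weeks 48, 96, 144) or two.
- Per dose: 64 × 3 = 192 tests, or 192 / 220.3 = 0.87 per PY; 64 × 2 = 128 tests, or 0.58 per PY.
- Placebo: none scheduled for continuing subjects; 48 × 0.05 = 2.4 at premature discontinuation, or 2.4 / 11.0 = 0.22 per PY.

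**Test-driven rate per 100 PY** = tests × q / PY × 100

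| q | Drug, 3 rounds (events) | Drug, 2 rounds (events) | Placebo, discontinuation tests only |
|---|---|---|---|
| 0.5% | 0.44 (0.96) | 0.29 (0.64) | 0.11 |
| 1% | 0.87 (1.92) | 0.58 (1.28) | 0.22 |
| 2% | 1.74 (3.84) | 1.16 (2.56) | 0.43 |
| 3% | 2.61 (5.76) | 1.74 (3.84) | 0.65 |

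The expected difference with three rounds is therefore 0.44 − 0.11 = 0.33 to 2.61 − 0.65 = 1.96 per 100 PY. With two rounds it is 0.29 − 0.11 = 0.18 to 1.74 − 0.65 = 1.09. Discontinuation tests on drug are left out and would add to the drug side.

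**Planned interval.** Take 0 placebo events and a Poisson variance for the drug rate (the SAP does not give the variance formula). The 95% CI is then rate ± 1.96 × √events / 220.3 × 100. With three rounds and q = 3% it is 0.48 to 4.75. In general it excludes 0 only when events exceed 1.96² = 3.84. That means q just above 2% for 192 tests (3.84/192) and just above 3% for 128 tests (3.84/128). With two rounds the interval therefore includes 0 across the whole assumed range.

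**Placebo precision.** Zero events in 11.0 PY has an exact upper 97.5% limit of −ln(0.025) / 11.04 × 100 = 33 per 100 PY. The normal approximation gives that side no uncertainty at all.

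**The case against.** The strongest reply is that the query's terms are not in the documents. If it already excludes latent TB and test-conversion terms, there is no bias. This stands, and the point is conditional on it.

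Second, active and latent TB can be told apart. Each event is reported as one or the other, SAP 10.2.3.3 gives rates by preferred term, and an active case leads to withdrawal and would appear in the discontinuation listing. So a reader who inferred that the rate measures testing instead of disease, or that an active case would be hidden, would go further than the documents allow. But SAP 10.2.3.3 plans no placebo difference by preferred term, so those rows do not correct the difference in SAP 10.2.3.1.

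Third, that difference sits in the overview section, where AESIs are one listed line. Applying it to each AESI category is a reading, not an explicit statement. If it is meant for all AESIs together, the same bias enters in diluted form.

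Fourth, the figures are upper bounds on an assumed yield. Subjects already positive are not required to be retested, and a negative repeat after an indeterminate result counts as negative. That a repeat-indeterminate result becomes an AE is inferred from two separate sentences. All of this stands, which is why the size is given only as a range.

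**Conclusion.** The testing schedule differs between the two sides of a planned long-term comparison, and the SAP does not allow for it. If the query includes latent TB, the long-term Tuberculosis rate carries roughly 0.4 to 2.6 test-driven events per 100 PY per dose with three rounds, or 0.3 to 1.7 with two, without any active TB. The difference from placebo, read as applying to each category, is then biased towards excess on drug. This rests on the assumed 0.5% to 3% yield, full retestability and 3.5 years without drop-out.

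Two stronger inferences are not supported. The difference is not positive by construction: discontinuation tests can produce placebo events, and the interval excludes 0 only at the upper end of the assumed yield. Nor does the problem reach the Period 1 difference in SAP 10.2.2.1, because all arms share one testing schedule there. The reporting rule itself is not at fault; the gap is in how the SAP counts what it produces. This is a cheap improvement.

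**What to change.** In SAP Table 13, define the Tuberculosis AESI as active TB and state the terms used. Add a separate row for latent TB and test-conversion events, including repeat-indeterminate results. In SAP 10.2.3.1, add a sentence that excludes this row from the long-term placebo difference and says whether the difference applies to each AESI category. Tabulation by test round is not needed.

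Cost: one extra table row and one sentence. No change to data collection, to the protocol's reporting rule or to TB management.
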